9.2.2 Study Subjects

According to the ACIP recommended immunization schedule for persons aged 0 through 18 years, MenACWY-CRM is recommended for children 2-23 months of age with high-risk conditions and other persons at increased risk of disease. This population includes:

- children with anatomic or functional asplenia (including sickle cell disease)
- children with persistent complement component deficiency
- children who travel to or reside in countries in which meningococcal disease is hyperendemic or epidemic
- children at risk during a community outbreak attributable to a vaccine serogroup.

There are approximately 500,000 births per year in California,[9] equivalent to nearly 1 million infants and toddlers age 2-23 months. There were approximately 38,000 babies delivered at KPSC facilities and contracting hospitals in 2012.

There were approximately 122,000 infants and toddlers age 2-23 months enrolled in the KPSC health plan in 2013. Among this population, there were approximately 30 individuals diagnosed with sickle cell, asplenia, or persistent complement deficiency.

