9.4.2 Operational Outcome Definition and Identification Process

Medical events occurring in emergency and inpatient settings within 6 months following a MenACWY-CRM vaccination will be searched in electronic medical records. Diagnoses occurring in any care setting (inpatient, outpatient, or emergency room) prior to the first dose of MenACWY-CRM vaccination will be searched in electronic medical records for evidence of pre-existing medical events.

Events with a history of the same diagnosis prior to the first dose of MenACWY-CRM vaccination will be excluded as a pre-existing condition. The medical records prior to the first dose of MenACWY-CRM will be searched for the same diagnosis code. As there will be a transition from International Classification of Diseases, Ninth Revision (ICD-9) to Tenth Revision (ICD-10) coding, in the event that the diagnosis following a MenACWY-CRM vaccination is coded using ICD-10, both the same ICD-10 code and an equivalent ICD-9 diagnosis code will be searched in the period prior to the first dose.

If a study subject is first seen in the emergency department and subsequently transferred to the hospital, this will be treated as a single episode of care. Multiple records of a single medical event will be consolidated and treated as 1 report.

Medical events are considered as eligible if they occur in eligible study subjects during the observation period and are not pre-existing conditions.

For each identified emergency department or inpatient visit the following information will be collected:

[figure not shown]
- Diagnosis of medical events
- Date of diagnosis: the date of the documented code after any dose of MenACWY-CRM vaccination is considered the date of diagnosis. The date of diagnosis is expressed as the number of days following the 1st, 2nd, 3rd, or 4th dose of MenACWY-CRM vaccination.
- Health care setting: hospitalization or emergency room visit

Process of medical events identification

Eligible medical events identification process is illustrated in Figure 1:

1. Children 2-23 months of age vaccinated with MenACWY-CRM will be identified by immunization records in electronic medical records.
2. Medical events will be searched up to 6 months following MenACWY-CRM vaccination in the electronic records of emergency department and inpatient care units in all medical centers of KPSC.
3. Diagnosis codes of medical events from these visits will be identified.

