9.8 Quality Control

9.8.1 Validation

Vaccination and medical event data will be extracted directly from the electronic medical record, which is the legal record of all medical care received within the KPSC system. Records of vaccinations and medical events can only be entered by medical staff, and are assumed to be an accurate representation of care received. No validation will be performed regarding vaccination. Medical events will be individually reviewed in order to determine the primary reason for the encounter as well as whether the condition predated the first receipt of MenACWY-CRM.

All data in the study is extracted and maintained in the electronic database at KPSC. The database is maintained on a daily basis, and undergoes quality validations regularly. Only authorized study personnel with passwords can access to databases. Validations of data in the study database will include range and consistency checks.

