5.1 Identification and review of events

Medical events occurring in ED and inpatient settings within 6 months following a MenACWY-CRM vaccination will be searched in the EMR.

Medical events will be characterized two ways: by encounter (hospitalization only, ED only, or both ED and hospitalization) and by diagnosis (see Appendix A, Table Shell 4 for details). The analysis allows for any recurrent events (i.e. different episodes of the same diagnosis) to be counted independently.

For characterization by encounter (Table 4a), all dates used for analysis will be the date of the ED encounter or hospital admission. Encounters will be considered pre-existing if all diagnoses made during the encounter are present in the medical record prior to the first dose of vaccine. Upon chart review by the study physician co-investigator, an encounter will be refuted if it is found to not be a true ED or hospital encounter. Each encounter will be reported as a single event, regardless of the number of diagnoses made during the encounter.

For characterization by diagnosis (Table 4b), all dates used for analysis will be the first date that the diagnosis is recorded in the EMR in any medical setting. A diagnosis will be excluded as pre-existing if the same ICD diagnosis code appears in any medical setting prior to the first dose of MenACWY-CRM vaccination. A diagnosis will be considered refuted if, upon chart review by the study physician co-investigator, there is no evidence of the diagnosis in the medical record. Multiple diagnoses associated with the same episode will be identified, but only the first diagnosis date (in any setting) will be counted in the analysis of each episode. Subsequent diagnoses for the same episode will be marked in Table 4b as “Diagnosis is continuation of an ongoing episode.” An episode will be considered as ended when there is symptom resolution as determined by chart review (e.g., symptoms stated to have resolved or the diagnosis/symptoms have been absent from the medical record before they are mentioned again). In the case of recurrent events, the date used will be the date of the first diagnosis in the medical record following resolution of the prior episode. Recurrent events will be marked in Table 4b as “Diagnosis is a recurrence”. Each diagnosis will be described independently. It is possible that different diagnoses from the same inpatient or ED encounter could have different diagnosis

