Appendix B: Underlying condition of vaccine indication

Vaccine recipients will be determined to have the following underlying conditions for vaccination if the associated diagnosis codes are present in the medical record six months prior to index vaccination, including the date of index vaccination.

1. Asplenia

Functional - Hemoglobinopathies (primarily sickle cell [SS or SC] disease)

ICD-9 Codes:

Diagnosis	ICD-9 Diagnostic Code
Sickle cell disease unspecified	282.60
HB-SS disease with crisis	282.62
Sickle cell thalassemia without crisis	282.41
Sickle cell/HB-C disease without crisis	282.63
Sickle cell/HB-C disease with crisis	282.64
Other sickle cell disease without crisis	282.68
Other sickle cell disease with crisis	282.69
Sickle cell thalassemia with crisis	282.42

ICD-10 Codes:

Diagnosis	ICD-10 Diagnostic Code
Sickle cell disease without crisis	D57.1
HB-SS disease with crisis, unspecified	D57.00
Sickle cell thalassemia without crisis	D57.40
Sickle cell/HB-C disease without crisis	D57.20
Sickle cell/HB-C disease with crisis, unspecified	D57.219
Other sickle cell disorders without crisis	D57.80

Other sickle cell disease with crisis, unspecified	D57.819
Sickle cell thalassemia with crisis, unspecified	D57.419
Hyposplenism	D73.0

Anatomic Asplenia

ICD-9 Codes:

Diagnosis	ICD-9 Diagnostic Code
Anomalies of spleen congenital	759.0

ICD-10 Codes:

Diagnosis	ICD-10 Diagnostic Code
Asplenia (congenital)	Q89.01
Congenital malformations of spleen	Q89.09
Acquired asplenia	Z90.81

2. Persistent Complement Component Deficiencies

ICD-9 Codes:

Diagnosis	ICD-9 Diagnostic Code
Other specified disorders involving the immune mechanism	279.8

ICD-10 Codes:

Diagnosis	ICD-10 Diagnostic Code
-----------	------------------------

Defects in the complement system	D84.1
----------------------------------	-------

Table 1: Study population selection

Population	Total (n)
Total number of persons within the KPSC cohort	
Total number of children 2-23 months old in the KPSC cohort	
Total MenACWY-CRM vaccine recipients among age 2-23 months	

Date tables created:

Period captured in the tables:

Report integrates the tables:

Table 2: Baseline Characteristics of MenACWY-CRM Recipients 2 to 23 Months of Age

Characteristic	Total	Number of doses received			
		One	Two	Three	Four
Age at first vaccination (months)	mean (sd) median Q1, Q3 (min - max)				
Age 2-6 months at first vaccination	n (%)				
Age 7-23 months at first vaccination	n (%)				
Gender					
Male	n (%)				

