Female	n (%)				
Underlying condition of index vaccine indication					
Persistent complement component deficiencies	n (%)				
Asplenia (functional, anatomic)	n (%)				
Unknown	n (%)				
Concomitant vaccinations	n (%)				
1 concomitant vaccination	n (%)				
≥ 2 concomitant vaccinations	n (%)				
vaccine 1	n (%)				
vaccine 2	n (%)				
Other*	n (%)				
Vaccinations <6 months prior to index	n (%)				
Any vaccination prior to index	n (%)				
vaccine 1	n (%)				
vaccine 2	n (%)				
Other*	n (%)				

* Includes all vaccines with less than 10 recipients

N/A = Not Applicable

† Any cell with count >0 but less than 3 is presented as "<<"

Table 3: Characteristics of MenACWY-CRM Recipients 2-23 Months of Age during the Observation Period

Characteristic	Total	Number of doses received			
		One	Two	Three	Four
MenACWY-CRM vaccination during observation period					
1 dose	n (%)				
2 doses	n (%)				
3 doses	n (%)				
Days from index vaccination to second dose	mean (sd) median Q1, Q3				
Days from second vaccination to third dose	mean (sd) median Q1, Q3				
Days from third vaccination to fourth dose	mean (sd) median Q1, Q3				
Other vaccines received during observation period					
Any vaccination during observation period	n (%)				
vaccine 1	n (%)				
vaccine 2	n (%)				
Other*	n (%)				
Other vaccines received concomitantly with subsequent MenACWY-CRM dose					
Any vaccination received concomitantly	n (%)				
vaccine 1	n (%)				
vaccine 2	n (%)				
Other*	n (%)				
Completed 6-month observation period following last dose	n (%)				
Duration of observation period (months) with censoring	mean (sd) median Q1, Q3 (min - max)				

* Includes all vaccines with less than 10 recipients during observation period

† Any cell with count >0 but less than 3 is presented as "<<"

N/A = Not Applicable

Table 4a: Summary of Hospitalization and Emergency Room Visit Event Identification and Review

Event	Automated Algorithm			Physician Review			Total Events for Analysis (g=a-b-e-f)
	Potential events identified (a)	Excluded events based on pre-existing condition (b)	Events remaining from automated identification (c=a-b)	Events confirmed (d)	Events refuted (e)	Confirmed events with diagnosis determined to be prior to index vaccination (f)	
Hospitalization only							
Emergency department only							
Emergency department and hospitalization							
Number of recipients experiencing a single hospitalization or emergency encounter							

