Number of recipients experiencing multiple different hospitalization or emergency encounters							
N/A = Not Applicable							

Table 4b: Summary of Diagnosis Identification and Review

Event	Automated Algorithm			Physician Review			Diagnosis is continuation of an ongoing episode (g)	Diagnosis is a recurrence (h)	Total Diagnoses for Analysis (i=a-b-e-f-g)
	Potential diagnoses identified (a)	Excluded diagnoses based on pre-existing condition (b)	Diagnoses remaining from automated algorithm identification (c=a-b)	Diagnoses confirmed (d)	Diagnoses refuted (e)	Confirmed events with diagnosis determined to be prior to index vaccination (f)			
Specific diagnoses									
diagnosis 1									
diagnosis 2									
Diagnosis groupings									
grouping 1									
grouping 2									
Number of recipients experiencing a single diagnosis									
Number of recipients experiencing multiple different diagnoses									

N/A = Not Applicable

Table 5a: Frequency and rate of hospitalization and emergency events observed following vaccination with MenACWY-CRM

Event	Overall		Number of vaccines received prior to event							
			One		Two		Three		Four	
	Frequency n (%)	Rate (95% CI)*	Frequency n (%)	Rate (95% CI)*	Frequency n (%)	Rate (95% CI)*	Frequency n (%)	Rate (95% CI)*	Frequency n (%)	Rate (95% CI)*
Hospitalization only										
Emergency department only										
Emergency department and hospitalization										

*Events per 1000 person years

Table 5b: Frequency and rate of diagnoses observed following vaccination with MenACWY-CRM

Event	Overall		Number of vaccines received prior to event								Setting of initial presentation with the diagnosis*						First occurrence or recurrence			
			One		Two		Three		Four		Inpatient		Emergency		Both settings		First occurrence		Recurrence	
	Frequency n (%)	Rate (95% CI)*	Frequency n (%)	Rate (95% CI)*	Frequency n (%)	Rate (95% CI)*	Frequency n (%)	Rate (95% CI)*	Frequency n (%)	Rate (95% CI)*	Frequency n (%)	Rate (95% CI)*	Frequency n (%)	Rate (95% CI)*	Frequency n (%)	Rate (95% CI)*	Frequency n (%)	Rate (95% CI)*	Frequency n (%)	Rate (95% CI)*
Specific diagnoses																				
diagnosis 1																				
diagnosis 2																				
Diagnosis groupings																				
grouping 1																				
grouping 2																				
etc.																				

*Events per 1000 person years

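### Neither exclusion step asks whether the acute episode began after dose 1, so new post-vaccination episodes can be kept or removed according to earlier coding and the wording of the review test

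*Protocol*

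**What the plan says.** Protocol 9.4.2 sets the eligibility rule: "Medical events are considered as eligible if they occur in eligible study subjects during the observation period and are not pre-existing conditions". Two steps put it into effect.

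- **Code search (column b).** SAP 5.1 states: "A diagnosis will be excluded as pre-existing if the same ICD diagnosis code appears in any medical setting prior to the first dose". There is no limit on how far back the search goes and no exception for an earlier episode that has resolved. An encounter is dropped only if every one of its diagnoses is already on record before dose 1.
- **Chart review (column f).** Under Protocol 9.8.1 the reviewer establishes the main reason for the encounter and also "whether the condition predated the first receipt of MenACWY-CRM". In the table shells of SAP version 2.0 the matching column is headed "Confirmed events with diagnosis determined to be prior to index vaccination (f").

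Both columns are subtracted before analysis. Table 4a ends in "Total Events for Analysis (g=a-b-e-f") and Table 4b in "Total Diagnoses for Analysis (i=a-b-e-f-g"). SAP 5.1 defines when a diagnosis is pre-existing by code and when it is refuted, but gives no rule for assigning a confirmed event to column f.

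The same section counts a new episode of the same diagnosis as a separate event once the previous episode has resolved.

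The groups for whom the vaccine is recommended (Protocol 9.2.2) begin with "children with anatomic or functional asplenia (including sickle cell disease"). SAP Appendix B lists "HB-SS disease with crisis" under codes separate from those for sickle cell disease without crisis.

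**The concern.** The objective is to describe emergency and inpatient events in the 6 months after vaccination. For a child with a lasting disease, the useful question is whether the acute episode behind the visit started after the dose. The plan asks instead whether a code, a diagnosis or a condition is older than the dose. For diseases that by nature precede vaccination, these questions can have different answers.

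Two faults follow. The protocol says *condition* and the SAP column says *diagnosis*, so two careful reviewers could treat the same admission differently. Separately, the code search applies a history rule that ignores resolution, although SAP 5.1 recognises resolution for repeat episodes that all fall after dose 1. At stake are the counts and rates in Tables 5a and 5b and the descriptions in Table 6. No sensitivity analysis is planned (SAP 5.4), and the limitations text mentions only pre-existing conditions that the search misses, not new episodes that it removes.

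**Working it through.** **Step 1: trace the rules.** The codes are from SAP Appendix B: D57.1 (sickle cell disease without crisis) and D57.00 (HB-SS disease with crisis, unspecified). Each child has a crisis diagnosis at an emergency or inpatient encounter within 6 months after a dose.

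| Child | On record before dose 1 | After dose 1 | Column b | Column f if *condition* = lasting disease | Column f if *diagnosis* = crisis |
|---|---|---|---|---|---|
| A | D57.1 only | D57.00 | passes | could be removed | kept |
| B | D57.00 at any time, resolved | D57.00, new episode | diagnosis removed | not reached | not reached |
| C | D57.1 only | D57.00, resolved, then D57.00 again | both pass | both could be removed | both kept, the second as a recurrence |

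B's post-dose crisis and C's second crisis are both new episodes after resolution. They are treated in opposite ways only because B's earlier crisis fell before dose 1. At encounter level, B's visit is lost at column b only if all its other diagnoses are also prior. For a mixed encounter that passes column b, nothing says whether one prior diagnosis is enough for column f.

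**Step 2: effect on the rate.** SAP 5.2 divides captured events by total person-time following doses. Events in columns b and f leave the numerator, and that formula makes no matching change to person-time. With s the share of otherwise eligible events removed in this way:

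reported rate = (1 - s) x true rate.

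**Step 3: reproduce the SAP's precision table.** SAP 3.2 assumes one person-year per child. The exact Poisson limits for x events are chi2(0.025; 2x)/2 and chi2(0.975; 2x+2)/2, divided by person-years. With x = 100 and 100 person-years this gives 81.4-121.6 per 100 person-years, as printed. All 12 cells of the table reproduce to within 0.1.

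**Step 4: use those limits as a yardstick.** The shares are assumptions; the documents give none.

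| Assumed s | Reported rate, true rate 100 per 100 person-years, N=100 | Exact 95% limits |
|---|---|---|
| 10% | 90 | 72.4-110.6 |
| 25% | 75 | 59.0-94.0 |
| 50% | 50 | 37.1-65.9 |

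The reported rate falls below the SAP lower limit when s exceeds 1 - 81.4/100 = 18.6%. At N=50 the lower limit is 74.2 and the threshold is 1 - 74.2/100 = 25.8%.

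At a true rate of 10 per 100 person-years and N=100 the SAP interval is 4.8-18.4. A 50% loss gives 10 x 0.5 = 5.0, still inside; the threshold is 1 - 4.8/10 = 52%. At 1.0 or 0.1 per 100 and N=100 the lower limit is 0.0, so no loss can take the rate below it.

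**The case against.** The strongest reply is that the SAP's working text favours the narrower reading of the review test. In the full sentence of Protocol 9.8.1, *the condition* most naturally refers back to the main reason for the encounter, which here is the crisis. Column f speaks of a diagnosis, and SAP 5.1 dates and describes each diagnosis on its own. A crisis first diagnosed after dose 1 would then survive. This stands. A reader might infer that chart review strikes out every complication of a qualifying disease, but the documents do not support that: it is one possible reading of undefined wording.

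The code search is also openly pre-specified. At encounter level it spares any visit with one newly coded diagnosis. In a child vaccinated from 2 months of age, little earlier record exists to search. These points limit the effect but do not explain why a resolved earlier episode disqualifies a new one only when it fell before dose 1.

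A reader might also infer that a cluster of complications after a dose would be invisible. That goes too far. Table 4b shows the counts in columns b and f for each diagnosis, although without dose timing or rates.

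The footnote in SAP section 8 restricts per-event tables to recipients with no history of that event. Applied to denominators, it would soften the effect on diagnosis-specific rates. It would also leave those children out of that analysis instead of showing their new episodes.

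**Conclusion.** The point holds in a limited form. Followed as written, the code search removes some diagnoses from acute episodes that begin after vaccination, and the review test could remove more if *condition* is read broadly. The emergency and inpatient events in Tables 5a, 5b and 6 can therefore be understated, and two children with the same post-dose episode can be treated differently because of an earlier code.

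The size cannot be computed from the documents. The rate falls by the fraction s, assuming unchanged person-time. Whether that matters against the study's own precision depends on the event rate: at N=100 a share above 18.6% matters at 100 per 100 person-years, while a 50% share stays within the interval at 10 per 100. A reader might infer a large, known bias, or that the plan names worsening of the underlying disease as a leading safety concern. The documents support neither. The case rests on the rule itself and its mismatch with the SAP's own handling of recurrence.

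**What to change.** 1. Align Protocol 9.8.1 and column f of Tables 4a and 4b on one test: *whether the acute episode that led to the encounter began before the first dose*.
2. Apply the episode-resolution rule of SAP 5.1 to codes already present before dose 1. Keep a new episode that starts after dose 1 and flag it *new episode or complication of pre-existing condition*.
3. Show flagged events as a separate row in Tables 4a, 4b, 5a and 5b, so that rates can be read with and without them.

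The cost is a wording change in both documents, one flag on the review form, the extra table rows, and chart review of events now dropped automatically at column b. That added review should be small at the 60-100 high-risk children expected, with some more if children vaccinated for travel or an outbreak are included. The total rate will then contain events driven by the underlying disease, which the separate row makes visible.

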9.8.2 Record Retention

The participating HMO's standard procedures for medical record and data file retention will be used for this study.

9.9 Limitations of the Research Methods

This is a descriptive, observational study conducted in a routine medical care setting. The decisions to use MenACWY-CRM and other vaccinations are independently made by HCPs and caregivers.

The validity of the study may be limited by several aspects. First, the generalizability will be limited by the characteristics of the population covered by KPSC. KPSC has a larger proportion of Hispanics compared to the US population, but it is broadly representative of the California population. Second, the study may not be able to capture all medical events following Men ACWY-CRM vaccination, due to children moving out of the KPSC region. Given that the population is relatively stable, it is less likely that the study will be affected. Finally, medical events described in the study will be severe due to the nature of diseases requiring inpatient and emergency room visits.

